**Here is a sample of what a patient-facing eSyM screen might look like:**

How OFTEN did you have PAIN?

Never    Rarely    Occasionally    Frequently    Almost constantly

BACK    CONTINUE    FINISH LATER    CANCEL

Please remember that this system is not monitored 24 hours a day. Please call your care team if your symptoms are severe.

**Here is a summary of the eSyM functionalities that will be designed and built:**

The main patient-facing tools will include the following (accessed via computer or app):
1. Alerts → Reminders about when to complete PRO reporting
2. Symptom Reporting → Surveys that will allow patients to report outcomes for modified PRO-CTCAE items
3. Visualizations → Display previously reported PROs
4. Education → Evidence-based symptom management tools (see appendix T)
The main clinician/staff-facing tools will include (accessed via computer or app):
1. Messaging → Message notifying when critical PROs have been reported
2. Visualizations → Display previously reported PROs for a given patient, highlighting critical symptoms
3. Reports → Display patients who are enrolled in the program, view results of multiple patients, and identify patients who did not report PROs on schedule

**Activity 3: Pilot test eSyM**

**Brief description of activity:** eSyM will be UAT/pilot tested at up to 6 sites. The primary purpose of UAT/pilot testing is for the research team to observe patients, clinicians, and staff interacting with the new system, identify challenges, and iteratively refine the system, training materials, or clinic workflow prior to the launch of the full-scale pragmatic stepped-wedge cluster randomized trial.

**SIV (Site Initiation Visit):** The SIV, protocol, and eSyM training is critically important to the success of the pilot study. All involved staff (on the research team and clinical teams) will be required to complete training using the materials and methods developed via Activity 2.

Training activities include:

- Training clinicians and clinic staff at each site on new clinic workflow SOPs.
- Training clinicians and clinic staff on how to get a patient set up with eSyM.
- Training each user audience (clinicians and patients) how to use their eSyM interface.
- Training informatics/IT staff at each site how to support and maintain eSyM.

*\*\* See appendices AA through LL for study resources. Please note – training materials and project resources will be routinely updated and branded to meet site needs.*

### **Activity 3 Population:**

- Age  $\geq$  18 years
- Priority population will be patients who meet one of the following:
  - Suspected thoracic cancer AND is inpatient following thoracic surgery.
  - Suspected gastrointestinal cancer AND is inpatient following gastrointestinal surgery.
  - Suspected gynecologic cancer AND is inpatient following gynecologic surgery.
  - Diagnosis of thoracic cancer AND scheduled to start a new treatment plan for thoracic cancer.
  - Diagnosis of gastrointestinal cancer AND scheduled to start a new treatment plan for gastrointestinal cancer.
  - Diagnosis of gynecologic cancer AND scheduled to start a new treatment plan for gynecologic cancer.
- Total population allowed to use eSyM:
  - Any patient at any participating site.

*\*\*Please note – Patients undergoing thoracic, gynecologic, or gastrointestinal surgery may not be diagnosed with cancer. These patients are still eligible for eSyM usage, questionnaire completion, and medical record abstraction.*

### **Activity 3 population will be operationalized as follows:**

- To determine if a patient has a diagnosis of one of the above cancer types, use ICD-10 diagnosis codes: 15.0-16.99 (esophago-gastric) C17.0-C21.9 (small int. colorectal) C22.0-24.9 (hepatobiliary) C23-C25.9 (pancreas), C34-34.9: lung, C53.0-53.9 (cervix) C54-54.9 (uterine) and/or C56-57.9 (ovarian). When it comes time to execute, this list may be modified. CPT and procedure codes and EPIC's OPTIME operating room scheduling module will be used to determine if a patient is scheduled for a priority surgery.

**Mode of Participation:** Patients will have a *choice* of their preferred mode of eSyM participation and switching can be accommodated. Patients with a smart phone will be offered that approach first. Alternatives include participation in eSyM via any web-enabled device (laptop/tablet/desktop). Patients may designate a caregiver willing to elicit their symptoms and

report responses on their behalf (proxy reporting). This flexibility facilitates the intervention's reach to frail patients who may be those most likely to benefit. As needed, patients will also be offered eSyM training through in-person, phone, and/or virtual visits.

**Number of subjects (per site and overall):** For Activity 3, user acceptability testing (UAT) will be done with up to 390 patients from up to 6 participating sites. At the lead site (Dana-Farber), we anticipate conducting UAT with 90 participants distributed as follows: 15 patients from each cancer/type modality combination (15 thoracic surgical, 15 gynecologic surgical, 15 GI surgical, 15 thoracic medical oncology, 15 gynecologic medical oncology, and 15 GI medical oncology). We anticipate that at each of the 5 remaining participating sites, each site will conduct UAT with up to 60 participants distributed as follows: 10 patients from each cancer/type modality combination (10 thoracic surgical, 10 gynecologic surgical, 10 GI surgical, 10 thoracic medical oncology, 10 gynecologic medical oncology, and 10 GI medical oncology). Protocol does not mandate equal distribution of participants among participating sites. If a site is running behind or facing lower than anticipated accrual to the activity, then the other sites may enroll additional participants to make up the difference until the study wide UAT goal has been reached. The numbers referenced above are meant to serve as an estimate and sites may suspend or continue UAT as needed.

**Materials that will be used to recruit subjects:** None.

**Duration anticipated to enroll all study subjects:** We anticipate that it will take three months prior to eSyM launch at each site to enroll all UAT/pilot participants, but the actual duration may vary.

**Monitor subjects for safety or minimize risks:** The risk to participants is minimal with the primary risk being loss of confidentiality/privacy. To monitor the risk of loss of confidentiality/privacy, the informatics/IT team will routinely monitor eSyM and investigate inquiries from study teams. Furthermore, patients who report severe symptoms will be prompted to call their clinic immediately, and clinicians will receive in-basket notifications in the Epic EHR of the severe symptom report.

### **Activity 3a: eSyM Usage**

#### **Human Subjects Research Category (NHSR, exempt, expedited, full review): NHSR/QI**

Because eSyM will be implemented at each site *for use in routine clinical care and because this is a quality improvement (QI) activity, this is not human subjects research.*

**Informed Consent: Waiver of consent.** When a patient becomes eligible for eSyM, he/she/they will receive an automated welcome message, which includes an electronic disclaimer that contains important information about the purpose of eSyM, how/when it should be used, and what it does and does not communicate to their care team (see Appendices N & Q).

**Methods that will be used to identify potential subjects:** Access to eSyM will be automated. EPIC will automatically deliver the invitation to use eSyM to all patients defined above (See Section: “Activity 3 population will be operationalized as follows”).

**Duration of subject’s participation in the study:** Per protocol, eSyM usage continues for up to 60-180 days from their trigger event (i.e., new chemotherapy treatment plan and/or surgery), but extended use of eSyM is at the discretion of the site and each patient participant.

#### **What data will be collected and how:**

- Participant responses to the symptom reporting questions within eSyM will be collected.
- Clinician responses to symptom reports will be collected.
- Data on eSyM usage by all user types will be collected.

**Long-term follow-up:** We will follow patients for 1-year after the trigger event (i.e., new chemotherapy treatment plan and/or surgery) for outcomes data captured via medical record abstraction.

### **Activity 3b: User Acceptability Testing (UAT)**

**Informed Consent: Waiver of documentation of consent.** Before observing the patient using eSyM, the patient will be provided with a letter (see appendix O) with the elements of informed consent, as well as the option not to be observed. They will be notified that participation is completely voluntary and can be stopped at any time for any reason. This activity is minimal risk.

**Methods that will be used to identify potential subjects:** Under a HIPAA waiver, study staff will look in the scheduling views of the electronic medical record and scheduling systems to identify potential participants. Study staff may also query Epic, administrative/operations/billing databases, order entry databases, and/or cancer registry databases to identify potential participants. Study staff may also accept potential patient referrals from site clinicians. Purposive sampling based on data from the electronic medical record (e.g., demographics, cancer stage, number of recent hospitalizations, number of prescription drugs) will be used to ensure that perspectives of diverse patients are included. Ideally, sites will use the developed eSyM reporting workbench reports in Epic to automatically pull a patient list for UAT.

**When, where, and how potential subjects will be recruited:** The clinical/study staff will approach the patient to see if they would be interested in participating in UAT. If a patient is interested in participating, the site will present the participant with a study letter and then begin observations. Patients may be approached in-person, via phone, via email or through a virtual visit.

**Description of procedures being performed for UAT:** Surgical patients will be set up to use eSyM at the time of surgical discharge (or at the site's discretion). Medical oncology patients will be set up to use eSyM at the time of their first chemotherapy dose visit (or at the site's discretion). The study staff will observe the patient accessing eSyM, the patient being trained on how to use eSyM, the patient using eSyM to do their first symptom reporting session.

**Duration of subject's participation in the study:** Per protocol, UAT observation will last approximately 30 minutes or less.

**What data will be collected and how:** The study staff will write down their observations as well as staff/patient feedback (see appendix P).

**Study design:** User acceptability testing.

**Long-term follow-up:** None. UAT is a one-time 30-minute session.

### **Activity 3c: Medical record abstraction**

**Informed Consent: Waiver of consent** to conduct medical record (and/or local cancer registry) reviews/Epic queries on all patients in the UAT/pilot to ascertain demographics and outcomes.

**Methods that will be used to identify potential subjects:** Automated and/or manual medical record (and/or local cancer registry) review will be done on all UAT/pilot patients.

**When, where, and how potential subjects will be recruited:** All participants in the UAT/pilot will undergo medical record (and/or local cancer registry) reviews. The medical record (and/or local cancer registry) reviews will be accomplished using both automated data extraction and manual data abstraction.

**What data will be collected and how:**

- Study-related health information and outcomes will be collected via medical record (and/or local cancer registry) review (automated and manual).
- Data will be submitted to the coordinating site (Dana-Farber) via REDCap or SFTP.

**Study design:** Medical record abstraction (both manual and automated).

**Long-term follow-up:** The patients' medical record may be reviewed for outcomes for up to 1-year after the trigger event (i.e., new chemotherapy treatment plan and/or surgery).

## **Activity 4: Pragmatic stepped-wedge cluster randomized trial**

**Brief description of activity:** A multisite, pragmatic stepped-wedge cluster randomized trial will be conducted in order to determine the effectiveness of eSym on health outcomes including: healthcare utilization, measured by the need for emergency and acute care; impact on cancer care delivery, specifically chemotherapy treatment duration and delays; patients' outcomes, indicated by levels of self-efficacy and symptom burden; and patients' satisfaction with their cancer care.

### **The trial involves patients in five ways:**

- 1) Patients assigned to eSym (eSym+) will report their symptoms via the eSym questionnaires delivered through MyChart. Patients are strongly encouraged to report their symptoms at home/between clinic visits with eSym. Study teams and clinicians may elect to ask eSym-eligible patients to complete eSym questionnaires in the clinic via a table, computer, and/or mobile device if patients have difficulties reporting or decline to report at home. Site study teams should consult the central study team before they initiate this workflow.
- 2) A subset of eSym+ patients will be asked to complete a research questionnaire called the “SASS Questionnaire (eSym+ or eSym+ Non-Responder version)” asking about their Self-efficacy, Attainment of information needs, Symptom burden, and Satisfaction with care (see PROMIS, CAHPS, IAM/AIM question banks – Appendices C through G). The eSym+ version is for patients who were assigned to eSym and completed at least one eSym questionnaire. The eSym+ Non-Responder version is for patients who were assigned to eSym but never completed an eSym questionnaire. The questionnaires will stop being administered once a minimum of 1,980 total surveys have been received in accordance with the following breakdown:

SASS Questionnaire accrual numbers							
	Surgery			Medical Oncology			Totals
	eSym+ Version	eSym- Version	eSym+ Non- Responder Version	eSym+ Version	eSym- Version	eSym+ Non- Responder Version	
Site 1	75	75	15	75	75	15	330
Site 2	75	75	15	75	75	15	330
Site 3	75	75	15	75	75	15	330
Site 4	75	75	15	75	75	15	330
Site 5	75	75	15	75	75	15	330
Site 6	75	75	15	75	75	15	330
Totals	450	450	90	450	450	90	1,980

- 3) Select patients NOT assigned to eSym (control group, eSym-) will also be asked to complete the “SASS Questionnaire (eSym- version)” (see Appendices U-X). Both Drug Therapy and Surgical Recover Experience eSym- versions will not ask questions evaluating eSym as the cohort will not be exposed to eSym at the time of the survey. The

questionnaire will stop being administered once a minimum of 1,980 total surveys have been received in accordance with the above breakdown. **\*\* Total number of SASS participants through surveys can be larger or smaller depending on availability.**

- 4) A small subset of eSyM- and eSyM+ patients will be invited to take part in follow-up qualitative interviews. See table below for recommended recruitment accrual. The interviews will be conducted following a developed interview guide (Appendix RR). Patients may or may not have previously completed SASS or eSyM questionnaires. Interviews will continue until thematic saturation is reached, or until 100 interviews are completed, whichever is first.

Patient Qualitative Interviews	
Site	Recommended Minimum Patient Interview Accrual
Site 1	4
Site 2	4
Site 3	4
Site 4	4
Site 5	4
Site 6	4
Total	24

*Total accrual can be larger or smaller depending on patient availability and interest. No more than 100 interviews will be conducted study-wide. Protocol does not mandate equal distribution of participants among sites.*

- 5) Regardless of whether a patient is assigned to eSyM+, eSyM-, or eSyM+ Non-Responder, and regardless of whether a patient completes the SASS Questionnaire or not, we are requesting a waiver of consent and HIPAA waiver to conduct medical record (and/or local cancer registry) reviews/Epic data queries on all patients in the denominator (for the definition of “denominator”, please see the section “how to operationalize the denominator” below) to ascertain demographics and outcomes. Because eSyM has QI implications and is part of routine clinical care, we must be able to compare responders with non-responders and eSyM+ with eSyM- and the combinations thereof to inform implementation beyond this initiative.

## **Informed Consent:**

### **Activity 4a: eSyM Usage (eSyM+): NHSR/QI.**

Because eSyM will be implemented at each site *for use in routine clinical care and because this is a quality improvement (QI) activity, using eSyM is not human subjects research, and therefore does not require consent*. When a patient becomes eligible for eSyM, he/she/they will receive an automated welcome message with a disclaimer that contains important information about the purpose of eSyM, how/when it should be used, and what it does and does not communicate to their care team (see Appendices N & Q).

### **Activity 4b: SASS QUESTIONNAIRE PARTICIPANTS (eSyM+, eSyM-, and eSyM+ Non-Responder): Waiver of documentation of consent.**

Eligible patients will receive a study letter in-person, by email, and/or by postal mail asking them to consider participating in a questionnaire that asks about their self-efficacy, attainment of information needs, symptom burden, and satisfaction with care (see Appendix Z). This invitation will include the elements of informed consent (see Appendix R). The study letter will notify participants that the questionnaire is completely voluntary and can be stopped at any time for any reason. The letter will be sent from the health system where the patient receives care and signed by the site PI. For example, a patient at Dartmouth will receive a letter/email inviting participation from Dartmouth signed by [name] and a patient from West Virginia University will receive a letter/email inviting participation from [name]. The letter includes a statement that survey completion has no influence or impact on a patient's medical care. This activity is minimal risk.

### **Activity 4c: MEDICAL RECORD REVIEW: Waiver of consent.**

Waiver of consent to conduct medical record (and/or local cancer registry) reviews/Epic queries on all patients in the “denominator” to ascertain demographics and outcomes regardless of whether a patient is assigned to eSyM+ or eSyM- and regardless of whether a patient completes the questionnaire or not. Because eSyM has QI implications and is part of routine clinical care, we must be able to compare responders with non-responders and eSyM+ with eSyM- and the combinations thereof to inform implementation beyond this trial. The medical record review meets all the conditions to obtain a waiver of consent (i.e., not FDA-regulated, involves no more than minimal risk, waiver will not adversely affect the rights and welfare of the subjects, and activity could not be practicably carried out without a waiver).

### **Activity 4d: PATIENT QUALITATIVE INTERVIEWS: Written informed consent.**

Eligible patients will receive a study letter in-person, by email, by Epic MyChart portal message, and/or by postal mail inviting them to participate in a qualitative interview that asks about their experiences with and feedback about the eSyM program and/or their care experience. This invitation will include a written consent form (see Appendices QQ & SS), which will be signed by the participant. Informed consent can be obtained through wet ink (returned in-person or via snail mail) or e-consent through REDCap. The provided study letter and consent form will notify participants that the interview is completely voluntary and can be stopped at any time for any reason. The consent form will also request patient approval for their contact information (name,

email, address, and phone number) to be shared with the coordinating center (Dana-Farber Cancer Institute) for the purposes of conducting the interviews. All patient qualitative interviews will be conducted by the study team at the coordinating center, who will reach out to the patient once the signed consent form is received. The study letter and consent form will be sent from the health system where the patient receives care and signed by the site PI. For example, a patient at Dartmouth will receive a letter/email inviting participation from Dartmouth signed by [name] and a patient from West Virginia University will receive a letter/email inviting participation from [name]. The letter includes a statement that survey completion has no influence or impact on a patient's medical care. This activity is minimal risk.

**Methods that will be used to identify potential subjects:** The denominator will be identified algorithmically; eSyM/MyChart/REDCap will be programmed so that the correct patients will automatically receive an invitation to use eSyM. When manual support is needed, under a HIPAA waiver, study staff will run reports in Epic, administrative/operations/billing databases, order entry databases, and/or cancer registry databases.

Under a HIPAA waiver, study staff will run reports in Epic as part of the eSyM registry and/or to identify patients meeting eSyM registry criteria to identify medical and surgical patients for eSyM+, eSyM-, eSyM+ Non-Responder SASS questionnaires, and patient qualitative interviews. Select eSyM- patients will be identified and surveyed before eSyM's launch at their site but after the registry has been created, ensuring that they have never been exposed to the program but would have been eligible to use it. Patients eligible to complete the eSyM- questionnaire will be identified using the patient registry and/or a site-developed Epic report to identify patients who had a qualifying surgery or new chemo start within the last 6 months. Patients eligible to complete the eSyM+ and eSyM+ Non-Responder questionnaires will be identified using the registry after eSyM has been launched at their site and 30-60 days after their surgery or new chemotherapy. The eSyM+ SASS questionnaire will be distributed to patients who were assigned to eSyM and completed at least one eSyM questionnaire. The eSyM+ Non- Responder SASS questionnaire will be distributed to patients who were assigned to the eSyM program but never completed an eSyM questionnaire. Sites may begin distributing eSyM+ and eSyM+ Non- Responder questionnaires as soon as they are able to do so after go-live and will continue until a minimum of 75 eSyM+ surveys and a minimum of 15 eSyM+ Non-Responder surveys have been collected for the medical oncology and surgery versions. Patients eligible to participate in the qualitative interviews will be identified using Epic reports and invitations will be sent to patients meeting eSyM program eligibility. Patients may or may not have previously completed SASS or eSyM questionnaires. Interviews will be conducted until thematic saturation is reached, or until 100 interviews have been completed, whichever is reached first.

In addition, under a HIPAA waiver, email and postal addresses will be obtained for all eSyM+, eSyM-, eSyM+ Non-Responder and qualitative interview patients. Email and postal addresses will be utilized to share the SASS questionnaire invitation through REDCap and/or mailing (see Appendix Z) and to send the interview invitations and consent forms via email and/or mailing (see Appendix SS and QQ).

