**Duration of subject's participation in the study:**

- 1) Per protocol, eSyM usage continues for up to 60-180 days but can continue indefinitely at the site's discretion.
- 2) The SASS Questionnaire is a one-time, 20-minute survey administered 30-180 days after surgery or first dose of chemotherapy.
- 3) The patient qualitative interview(s) will last approximately 30 (but no more than 120) minutes; they will be administered any time after eSyM assignment at a time that is convenient for the subject.
- 4) All eSyM- control and eSyM+ intervention patients will be followed for outcomes for up to 1-year after the trigger event (i.e., new chemotherapy treatment plan and/or surgery).

**Duration anticipated to enroll all study subjects:** We anticipate that it will take five years to complete this activity.

**Study design:** Hybrid effectiveness-implementation stepped-wedge cluster randomized trial.

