**Description of all research procedures being performed:**

- a) Epic, administrative/operations/billing databases, order entry databases, and/or cancer registry databases may be queried to identify denominator patients under a HIPPA waiver.
- b) Patients assigned to eSyM+ will be set up to use eSyM by their local clinic/study staff. Surgical patients will be set up to use eSyM at the time of surgical discharge (or at the site's discretion). Medical oncology patients will be set up to use eSyM at the time of their first chemotherapy dose visit (or at the site's discretion).
- c) Select eligible participants will receive a message inviting them to participate in the SASS questionnaire 30-days after surgery or first chemo dose (Appendix Z).
- d) Participants who participate in the SASS questionnaire and indicate that they wish to receive a gift card will receive \$15 gift card. Gift cards will be mailed or emailed according to patient preference. Please note, emailed gift cards will come directly from Amazon.com or sent by a study research staff member.

- e) Participants who participate in the qualitative interviews and indicate that they wish to receive a gift card will receive a \$15 gift card. Gift cards will be mailed or emailed according to patient preference. Please note, emailed gift cards will come directly from Amazon.com or sent by a study research staff member.
- f) All denominator patients (eSyM- control and eSyM+ intervention) will undergo medical record (and/or local cancer registry) reviews. The medical record (and/or local cancer registry) reviews will be accomplished using both automated data extraction and manual data abstraction under a HIPAA waiver.

**Monitor subjects for safety or minimize risks:** The risk to participants is minimal with the primary risk being loss of confidentiality/privacy. To monitor the risk of loss of confidentiality/privacy, the informatics team will routinely monitor eSyM reports and data extracts and investigate inquiries from study teams. Furthermore, patients who report severe symptoms will be prompted to call their care team immediately, and clinicians will receive in-basket notifications in the Epic EHR of the severe symptom report. All interview participants from outside of Dana-Farber Cancer Institute will provide written consent to have their information shared with the Dana-Farber research staff members who will contact them to conduct the interviews.

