The questionnaire will stop being administered once a minimum of 1,980 total surveys have been received in accordance with the above breakdown. (**Table 4**) *** Total number of SASS participants through surveys can be larger or smaller depending on availability.*

A small subset of eSyM- and eSyM+ patients will be invited to take part in a one-time qualitative interview. Patients may or may not have previously completed SASS or eSyM questionnaires. Interviews will continue until thematic saturation is reached, or until 100 interviews are completed, whichever is reached first.

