- Using these results, the difference between the intervention condition (eSyM+) and the control condition (eSyM-) along with a corresponding 95% confidence interval will be calculated for each site. In addition, using the point estimates from the six sites, we will calculate the coefficient of variation of the difference between conditions.
- We will then estimate the overall between-conditions difference integrating the site-specific differences. Specifically, a weighted average and corresponding 95% confidence interval will be calculated, using the site-specific point estimates their standard error estimates, where the reciprocal of the site-specific variance estimates will be used for the weights.
- In addition, generalized linear models (GLMs) will be used to investigate factors associated with the outcome. In the GLMs, we will include the intervention indicator, “site” and other factors (i.e., age (at cancer diagnosis for medical oncology patients and at index surgery for surgical patients), sex, employment status, education, ability to pay bills, and technology confidence) as independent variables. For modeling continuous outcomes, we will employ the identity link function. For dichotomous outcomes, the logit link function will be utilized. Note that, when more appropriate (where some subjects have data from both pre- and post-intervention periods), we will use GLMMs by treating “subject” as random-effects instead of GLMs for some outcomes.

Analysis of Outcomes classified as Type 4:

- We will estimate the intervention effect on each outcome.
- To this end, analyses similar to those for Aim 2a (see Section 4) will be conducted. GLMMs will be used with the identity link function for continuous outcomes and with the logit link function for dichotomous outcomes. The intervention effect will be summarized as the mean difference and odds ratio for continuous outcomes and dichotomous outcomes, respectively, and reported with a corresponding 95% confidence interval and p-value.

Interpretation of the PROMIS scores: Note that Yost and Cella have reported minimally important difference (MID) ranges for five PROMIS domains including fatigue, pain, depression, anxiety, and physical functioning^{17,18} Cella recommends using 0.5 SD as the MID for PROMIS scales^{19,20}

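### The SASS survey window differs by condition in one protocol passage and is common in others, and the PROMIS and CAHPS analyses do not account for time since surgery or chemotherapy start.

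*Protocol*

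**What the plan says.** Four places set the timing of SASS.

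- **Protocol 5.0, Activity 4, methods to identify potential subjects.** This is the only place that sets timing by condition. eSyM- patients come from the patient registry and/or a "site-developed Epic report to identify patients who had a qualifying surgery or new chemo start within the last 6 months". eSyM+ and Non-Responder patients are identified "using the registry after eSyM has been launched at their site and 30-60 days after their surgery or new chemotherapy".
- **Protocol 5.0, Activity 4, duration of participation.** No arm is named: "The SASS Questionnaire is a one-time, 20-minute survey administered 30-180 days after surgery or first dose of chemotherapy".
- **SAP 3.4.** It repeats that 30-180 day statement, again with no arm named.
- **Protocol 5.0, Activity 4, description of research procedures, item c.** Selected patients are invited to "participate in the SASS questionnaire 30-days after surgery or first chemo dose", with no distinction by arm.

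No text says which of these governs.

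The PROMIS items are Type 3 outcomes (SAP 6.1, Table 12). SAP 6.2 starts from crude means by condition and site, takes the eSyM+ minus eSyM- difference at each site, and combines the six: "a weighted average and corresponding 95% confidence interval will be calculated, using the site-specific point estimates", weighted by inverse variance. A supporting generalized linear model (GLM) includes the intervention indicator, site and age, together with "sex, employment status, education, ability to pay bills, and technology confidence) as independent variables". SAP 7.2 applies the same sampling and analysis to CAHPS.

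**The concern.** Pain interference, fatigue, physical function and self-efficacy can plausibly change over the weeks after an operation or across chemotherapy cycles. If controls may be surveyed up to six months after the trigger and eSyM+ patients at 30-60 days, survey timing is associated with condition. Where the same rule applies at each site, averaging over sites does not remove that association. The crude difference has no covariates, and the supporting GLM does not list days since the trigger. Neither SAP 6.2 nor SAP 7.2 plans matching, restriction or a sensitivity analysis on survey timing. The missing-data plan for PROMIS concerns absent scores only.

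The comparisons at stake are the SASS-based parts of Aims 2c and 2d. Symptom burden and care satisfaction are also among the outcomes in the Protocol's PICOTS table. A difference in timing could appear as an eSyM effect, or could mask one.

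**Working it through.** **The plan's own figure.** Per site: (75 + 75 + 15) for Surgery + (75 + 75 + 15) for Medical Oncology = 330. Over six sites, 330 x 6 = 1,980, which agrees with SAP 3.3 and Table 4. Per cohort this is 450 eSyM+, 450 eSyM- and 90 Non-Responder surveys. The SAP gives no power calculation for Aims 2c and 2d.

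**Timing under each reading.** The documents do not describe how surveys spread within a window. I assume an even spread, so the mean is the midpoint.

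| Reading | eSyM- window, mean | eSyM+ window, mean | Gap | Controls outside days 30-60 |
|---|---|---|---|---|
| Identification rule alone | 0-180, day 90 | 30-60, day 45 | 45 days | 1 - 30/180 = 83% |
| Identification rule with a 30-day floor | 30-180, day 105 | 30-60, day 45 | 60 days | 120/150 = 80% |
| 30-180 days governs every arm | 30-180, day 105 | 30-180, day 105 | 0 | not applicable |

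The 30-day floor widens the gap in the means. Only the third reading removes it.

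**How much drift would matter.** Assume an SD of 10 points, no eSyM effect, one cohort and 450 v 450 surveys. Then SE = 10 x sqrt(1/450 + 1/450) = 0.67, and the 95% half-width is 1.96 x 0.667 = 1.31 points. Bias = drift per 30 days x gap/30. The chance of a falsely significant difference follows from the normal approximation.

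| Assumed drift per 30 days | Bias (gap 45 to 60 days) | Chance of false significance (nominal 5%) |
|---|---|---|
| 0.25 point | 0.38-0.50 | 9-12% |
| 0.5 point | 0.75-1.0 | 20-32% |
| 1 point | 1.5-2.0 | 61-85% |

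The SD and the drift are assumptions, not figures from the documents. These biases all stay below the 0.5 SD minimally important difference cited in SAP 6.2, which is 5 points here.

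**Precision of a comparison restricted to days 30-60.** Count Non-Responders with eSyM+, giving 540.

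- All controls: 1.96 x sqrt(1/540 + 1/450) = 0.125 SD.
- Controls left after restriction: 450 x 30/180 = 75, or 450 x 30/150 = 90.
- Half-width with 75: 1.96 x sqrt(1/540 + 1/75) = 0.24 SD. With 90: 1.96 x sqrt(1/540 + 1/90) = 0.22 SD.

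**The case against.** The best defence is that there may be no imbalance. The arm-specific passage says how patients are identified. The 30-180 day statement says when the survey is administered, and it makes no distinction by arm. Protocol 10.0 points to the SAP as the most current plan, and SAP 3.4 has one common window. The six-month look-back would then simply be its upper end. eSyM+ patients identified at 30-60 days may also reply later, since email, post, phone and clinic are all allowed. The six-month limit may attach only to the site-developed report and not to the registry route, so practice could vary by site.

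This shows that the imbalance is conditional, but it does not settle the matter. The 30-180 day range also fits as an outer limit around the arm-specific rule, and then the asymmetry remains. The registry route carries no narrower window for controls.

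Three stronger readings are tempting, and the documents do not support them.

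- **A definite bias of known sign.** Multiplying the 83% of controls outside the window by an assumed 0.3 SD gives 0.25 SD. That requires every out-of-window control to differ in the same direction. With a 0-180 day window, 17% of controls (30/180) fall before day 30 and 67% (120/180) after day 60. Under steady recovery these two groups would partly cancel. Nothing in the documents shows that timing would hide a benefit in Surgery or create one in Medical Oncology.
- **Aims 2c and 2d cannot separate eSyM from timing.** Aim 2c also has outcomes that do not depend on SASS, such as MyChart activation and logins (SAP Table 12). For the SASS outcomes, the control window includes days 30-60, so adjustment is possible.
- **The dates needed are already held.** Service dates are listed under Activity 4c in Protocol 12.0. The Activity 4b list there names contact details and patient-reported responses, but no survey completion date.

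**Conclusion.** The point holds as a conflict between passages combined with an analysis that does not account for it. If the arm-specific identification rule is followed, the SASS-based PROMIS and CAHPS comparisons mix condition with time since the trigger. The mean gap is 45 days, or 60 with a 30-day floor, assuming an even spread in each window. If 30-180 days governs every arm, the expected gap is zero. The documents do not settle which reading applies.

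The size and direction of any bias in the scores cannot be determined from the documents. The drift figures only show that modest trends could matter against intervals this narrow. The primary endpoint, an emergency department treat-and-release event by Day 30, comes from the medical record and is unaffected. This should be fixed because it is a cheap improvement to secondary survey outcomes. It does not threaten the trial's main conclusion.

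**What to change.** 1. State one SASS window for all versions. Make Protocol 5.0, Activity 4 (identification, duration and procedures) and SAP 3.4 agree.
2. Confirm that the survey completion date is recorded, including for paper and phone responses, and can be linked to the trigger date.
3. Add days from trigger to survey to the Type 3 model in a flexible form such as a spline, separately for Medical Oncology and Surgery. Report the eSyM+ v eSyM- PROMIS and CAHPS differences from that adjusted model.
4. Report a comparison restricted to the overlapping 30-60 day window as a sensitivity analysis.

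The cost is SAP and protocol wording, one covariate and a check on date capture, with no new patients. The adjusted estimate will have somewhat wider intervals. The restricted comparison is much less precise, with a half-width of about 0.22-0.24 SD per cohort against 0.125 SD, so it should support the adjusted estimate and not replace it.
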